# 5. Ascites study

- (1) Ascites clinical study
  - a. Cell count, ascites culture, tuberculosis culture, protein, albumin, lactate dehydrogenase (LDH)
- (2) Ascites exploratory study
  - a. Flow cytometric analysis of ascites cells: the cells in ascites will be analyzed the expression percentage of CD3, CD4, CD8, CD 11, CD14, CD33, CD56, CD57 using specific antibodies.
  - b. Cell block: the cells in ascites will be prepared to be cell block and for HE staining, PD-L1 staining, tumor proportion score, combined positive score.
  - c. Perspective study: in order to examine which genetic trait is related to the response of malignant ascites to immune checkpoint inhibitor, we will sequence the exons of 341 cancer-associated genes and determine the deleterious mutation status. The total mutational burden (Teo MY, Clin Cancer Res 2017) will be executed using cell blocks from 4 patients (2 with good ascites response and 2 with ascites refractory to pembrolizumab/nivolumab).
- 6. Endpoints

Primary endpoint: reduction of malignant ascites. The ascites amount will be estimated by a five-point method developed by Oriuchi et al. (Oriuchi N, Jpn J Clin Oncol 2005; Maeda H, World J Gastroenterol 2015).

Secondary endpoints: ascites signs, ascites symptoms, safety and overall survival.

- (1) Ascites symptoms (anorexia, nausea, early satiety, vomiting, abdominal pain, abdominal swelling, dyspnea, fatigue, swollen ankles and heartburn) were assessed subjectively using a patient questionnaire with a four-point Likert scale (none, mild, moderate and severe) (Likert R, Arch Psychol 1932).
- (2) Ascites signs (abdominal distension dull to percussion, shifting dullness, fluid thrill and bulging flanks) were assessed objectively after abdominal examination by the investigator.
- (3) Overall survival of patients is defined as the period from the first dose of intraabdominal immune checkpoint inhibitor to the time of lost-of-follow or death, whichever occurs first.

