Both pembrolizumab and nivolumab have been administrated intraperitoneally without obvious toxicities in murine tumor models (Fessas P, Semin Oncol 2017; EMA report: pembrolizumab 2015; EMA report: nivolumab 2015). Pembrolizumab at a dose of 10 mg/kg given intraperitoneally on days 6, 10, 13, 16 and 20 after implantation led to tumor growth inhibition of 92.5% at day 20 in murine. Similarly, nivolumab at a dose of 10 mg/kg given intraperitoneally on days 7, 10 and 13 after implantation inhibited tumor growth by 76% at day 20.

At our hospital (China Medical University Hospital), about one hundred gastric cancer patients, 50 pancreatic cancer patients and 50 biliary tract cancer patients are registered and treated each year (Chiu CF, Gastroenterol Res Pract 2016; Chiu CF, Springerplus 2016, Report of Cancer Registration in China Medical University Hospital). Patients with advanced or metastatatic cancer are ultimately refractory to chemotherapy with or without targeted therapy. Among them, more than 20 patients suffer from intractable malignant ascites which is managed by repeated paracentesis with increasing frequency. Till now, there is no reported or ongoing clinical trial to investigate the efficacy of intraperitoneal checkpoint inhibitor on the malignant ascites. Based on the previous findings and the literature review, we propose to evaluate the efficacy of immune checkpoint inhibitor (pembrolizumab) on the malignant ascites of patients with advanced gastric, pancreatic and biliary tract cancers.

The major works in the 3-year-project are summarized as:

1. Screening the candidate patients. Patients who fulfill the inclusion and exclusion criteria will be

screened. The study purpose and protocol will be explained thoroughly by physicians. Study starts only if patient read, understand and sign the inform consent.

- 2. Intraperitoneal administration of immune checkpoint inhibitor (pembrolizumab or nivolumab) per protocol followed by scheduled evaluation.
- 3. Ascites studies: Ascites cells and malignant cells in ascites are to be analyzed using flow cytometry, immunohistochemical staining, exon sequencing and total mutational burden determination.
- 4. Correlation study using clinical characteristic, ascites data and clinical response.

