# 3. Exclusion criteria

- (1) Patients have ascites which is related to causes other than the malignancies
- (2) Patients who are receiving intraperitoneal treatment for their malignant ascites including therapeutic paracentesis
- (3) Patients with active infection
- (4) Patients with bleeding disorders
- (5) Patient with active cardiopulmonary disease or history of ischemic heart disease
- (6) Patients have intolerant abdominal pain
- (7) Patients who have serious concomitant systemic disorders incompatible with the study, i.e. poorly controlled diabetes mellitus, auto-immune disorders, cirrhosis of the liver, and the rest will be at the discretion of in-charged investigator
- 4. Procedure

- (1) Prior to the administration of first dose immune checkpoint inhibitor (pembrolizumab or nivolumab), ascites at least 200 ml will be collected by paracentesis. The ascites will be sent for examinations listed in "ascites study". The same procedure is repeated before each administration of immune checkpoint inhibitor.
- (2) At the first 3 patients, immune checkpoint inhibitor (pembrolizumab or nivolumab) will be administered intraperitoneally at a dose of 20 mg diluted in 100 ml normal saline through a temporary catheter in 10 min (reason seen below). If there is no grade 3 or higher toxicity, the dose of pembrolizumab / nivolumab will be escalated to 50 mg for subsequent dose.
- (3) If there is no grade 3 or higher toxicity for the initial 3 patients receiving first dose 20mg of immune checkpoint inhibitor, the first dose of pembrolizumab / nivolumab will be escalated to 50 mg for subsequent patient.
- (4) The estimated initial dose for pembrolizumab / nivolumab is based on the report that both compounds were given safely to murine at a dose of 10 mg/kg. Human Equivalent Dose (HED) is 10 divided by Km ratio 12.3 = 0.8 mg/kg (Nair AB, J Basic Clin Pharm 2016). For a man with a weight 60kg, the dose will be 48 mg. Although intravenous injection of either pembrolizumab or nivolumab is well tolerated at a dose up to 10 mg/kg in previous clinical study, we reduce the initial dose of intraperitoneal infusion to 20 mg for either pembrolizumab or nivolumab.
- (5) Remove the temporary catheter after infusion.
- (6) Repeat the above procedure every 2 weeks for 1-4 times depending on the response of ascites clinically.

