# 8. Assessment of response and toxicity

- (1) Prior to treatment, a medical history, physical examination, ascites symptoms, ascites signs, laboratory studies (blood cell count, electrolytes, liver and renal function tests, and urinalysis), chest radiography, and abdominal CT are performed.
- (2) Physical examination, ascites symptoms and ascites signs are assessed every week.
- (3) The amount of ascites is assessed by radiologists using CT which will be performed at 4th and 8th week after treatment.
- (4) Patients safety is assessed by adverse event reporting throughout the study. Adverse events

are graded according to the National Cancer Institute Common Toxicity Criteria (NCI CTCAE version 4.0).

- (5) For the analysis of the secondary endpoint, any patient lost to follow-up is censored at the time of last visit.
- 9. Correlation study of predictive factors: the association of ascites response and the characteristic of ascites, clinical features of patients and type of tumors will be analyzed.

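### Does measuring total mutational burden in only two good responders and two refractory patients call for a change to the protocol?

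*Protocol*

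**What the plan says.** All references are to the Protocol, Materials and Methods.

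- **Aim of item 5(2)c.** It is undertaken "in order to examine which genetic trait is related to the response of malignant ascites to immune checkpoint inhibitor".
- **Sequencing.** The same item continues: "we will sequence the exons of 341 cancer-associated genes and determine the deleterious mutation status". That clause names no number of patients.
- **Mutational burden.** The next sentence does name a number. Total mutational burden is to be determined "using cell blocks from 4 patients (2 with good ascites response and 2 with ascites refractory to pembrolizumab/nivolumab".
- **Sampling, item 4(1).** Before the first dose, "ascites at least 200 ml will be collected by paracentesis". Then: "The ascites will be sent for examinations listed in" the ascites study, which is section 5. The procedure is repeated before every later dose.
- **Section 9.** The correlation study says that "the association of ascites response and the characteristic of ascites, clinical features of patients and type of tumors will be analyzed".
- **Status.** Item 5(2) is headed as exploratory, and section 1 calls the trial a pilot. Section 6 names ascites reduction as the primary endpoint, with signs, symptoms, safety and overall survival as secondary endpoints. Mutational burden is not among them.
- **Sample size.** None is given. The Background offers one guide to numbers at the hospital: "more than 20 patients suffer from intractable malignant ascites" among those treated each year, in a three-year project.

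**The concern.** Item 5(2)c states an aim of association, then fixes a number of patients from which no association can be estimated. Choosing the four by outcome adds a second difficulty: a striking contrast between two good responders and two refractory patients is easy to over-read, and the item itself does not say that the result is descriptive.

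The limit also looks needless. If item 4(1) sends every patient's ascites for all the tests in section 5, the 341-gene sequencing would exist for everyone. A mutation count per patient could then enter the section 9 analysis with no further laboratory work, and the trial would obtain an estimate with a confidence interval in place of four case reports. What would be lost is exploratory information on a candidate predictor of response.

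**Working it through.** The protocol gives no calculation behind the number four, so there is no figure of its own to reproduce. There are three checks.

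**1. What two against two can show.** Input: group sizes 2 and 2, from item 5(2)c.

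- Number of arrangements: C(4,2) = 6.
- Smallest exact p: one-sided 1/6 = 0.167, two-sided 2/6 = 0.333.
- Probability of complete separation when burden is unrelated to response: 2/6 = 0.333.
- For comparison, 3 v 3 gives 2/20 = 0.10 and 4 v 4 gives 2/70 = 0.029. Four per group is therefore the smallest equal size that can reach 0.05.
- Clopper-Pearson 95% limits: for 2 of 2 the lower limit is √0.025 = 0.158; for 0 of 2 the upper limit is 1 − 0.158 = 0.842.
- A t-test that assumes normality (2 degrees of freedom, two-sided 5%) has 10% power at a difference of 1 SD and 22% at 2 SD. It needs about 5.7 SD for 80%.

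So the four patients support case description and nothing more.

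**2. What an all-patient count might add.** The sample size, the true correlation r between mutation count and ascites change, bivariate normality and a two-sided 5% level are all assumptions. Sizes of 10, 20 and 60 are taken; 60 is 3 years × 20 patients, the whole candidate pool at the Background figure. Power by simulation:

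| Analysis | n = 10 | n = 20 | n = 60 |
|---|---|---|---|
| All patients, r = 0.6 | 49% | 84% | 100% |
| All patients, r = 0.5 | 33% | 64% | 99% |
| All patients, r = 0.5, response split at the median | 20% | 42% | 91% |
| All patients, r = 0.3 | 13% | 26% | 65% |
| t-test on 2 best v 2 worst, r = 0.5 | 14% | 20% | 28% |

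An observed correlation of 0.5 has the 95% interval tanh(atanh(0.5) ± 1.96/√(n − 3)):

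- n = 10: tanh(0.549 ± 0.741) = −0.19 to 0.86.
- n = 20: tanh(0.549 ± 0.475) = 0.07 to 0.77.

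The gain over four patients is real if the data exist. At pilot sizes the result would still only generate hypotheses.

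**3. Whether the data exist.** Set items 4(1) and 5(2)c side by side.

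- Read literally, item 4(1) sends each sample for everything in section 5. That would include mutational burden in every patient, which item 5(2)c rules out by naming four. It would also require sequencing before each of up to four doses. Item 4(1) therefore cannot settle who receives the tests in item 5(2)c.
- Item 5(2)c has one purpose, and its only patient number is four. It can be read as sequencing for all with burden for four, or as a single four-patient sub-study.
- The stated output of the sequencing is whether deleterious mutations are present. The protocol does not say that burden is counted over the 341 genes, and it sets no minimum tumour-cell content for a sample. A count in every patient is possible, but it is not shown to be the planned measure.

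**The case for a change.** The best argument for a change is that the protocol itself fixed the number four in the same item that states an aim of association, so the choice cannot be put down to detail left for a statistical analysis plan. Grammatically the limit attaches only to the sentence on burden. The sequencing clause, the cell blocks in item 5(2)b and the lists of work in the Abstract and Background carry no such limit. On that reading one added factor in section 9 costs no extra sequencing, and the wording could be made conditional so that it serves either reading.

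Part of this stands. The 2 v 2 arithmetic is beyond dispute, the population to be sequenced is unclear, and saying who is sequenced would help. The rest does not carry a change:

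- Reading the sequencing as unlimited is permissible but not secure. If it is wrong, a count in all patients means new laboratory work.
- If it is right, mutation status is already a characteristic of the ascites within the scope of section 9. Whether it enters as a count, and with what interval, is ordinary analysis-plan detail.
- The power contrast compares two analyses that the protocol does not plan, and it varies widely with the assumed r, n and form of response.

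**Conclusion.** No change is needed. Mutational burden in four patients is a contrasting-case description, and an exploratory item in a pilot may reasonably stop there. A two-sided exact p that cannot fall below 0.333 would be a serious fault if a test were promised; none is. No primary or secondary endpoint depends on the item.

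The proposed gain holds only if all patients are sequenced. In that case analysts working under section 9 can use the results without an amendment. If only the four are sequenced, the remedy merely adds the word descriptive to a result already placed under an exploratory heading. On neither reading does the trial's conduct or its conclusions clearly alter.

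This rests on the text as it stands: no sample size, no definition of burden beyond a citation, and no explicit statement of who is sequenced. The last is a drafting ambiguity that the investigators can settle in a sentence if they wish. Whoever reports the four patients should list the individual values and draw no inference from them.

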# 7. Data Safety and Monitoring Plan

Data Safety and Monitoring Plan is set for ensuring the safety of patients. The plan is composed of three phases.

- (1) Screening and recruitment period
  - a. Screening patient by pre-set inclusion and exclusion criteria
  - b. Explain the current medical situation to patients, and alternative treatment methods
  - c. Obtain signed inform consent
- (2) Trial execution period
  - a. Conduction of study during hospitalization
  - b. Bedside monitoring by a physician or nurse from beginning till 10 min after administration of medication
  - c. Overnight monitoring
- (3) Follow-up period
  - a. Outpatient clinic every week till 2 weeks after the last dose of medication; then every one month for 6 m, then
  - b. Follow the patient every 2 m till end of life

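### The primary CT endpoint does not separate drug effect from fluid removed by paracentesis: CT–tap order, the origin of weeks 4 and 8, and on-study drainage are left open

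*Protocol*

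**What the plan says.** All references are to the numbered items under Materials and Methods in the Protocol.

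- **Endpoint (item 6).** The primary endpoint is "reduction of malignant ascites. The ascites amount will be estimated by" a five-point CT method. No threshold, time point or rule for removed fluid is attached.
- **Baseline (item 8(1)).** In the pre-treatment work-up, "chest radiography, and abdominal CT are performed". The order relative to the first tap is not given.
- **Follow-up CT (item 8(3)).** "The amount of ascites is assessed by radiologists using CT which will be performed at" weeks 4 and 8 after treatment. Neither the first nor the last dose is named as the origin.
- **Study taps (item 4(1)).** Before the first dose, "ascites at least 200 ml will be collected by paracentesis". This is a minimum, with no maximum stated. "The same procedure is repeated before each administration of immune checkpoint inhibitor".
- **Number of doses (item 4(6)).** "Repeat the above procedure every 2 weeks for 1-4 times depending on the response of ascites clinically".
- **Therapeutic drainage (item 3(2)).** It appears only as an entry exclusion: "Patients who are receiving intraperitoneal treatment for their malignant ascites including therapeutic paracentesis". Items 4 to 8 do not mention it after entry and do not require its date or volume.
- **Design (item 1).** A pilot study, with no control arm described.

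**The concern.** A CT volume reflects what has accumulated less what has been removed. Without a comparator, nothing in the design cancels the removed part, so the plan as written can count drained fluid as drug effect. A patient whose ascites is worsening, and who is drained heavily shortly before a CT, could be read as reduced. A baseline CT taken after the first tap would push the reading the other way. The same error would pass into the correlation study (item 9) and into the choice of two good and two refractory patients for mutational burden (item 5(2)c) if response there is judged by CT, which the protocol does not state.

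**Working it through.** The plan gives no figure on this point to reproduce. The check uses the schedule and a simple fluid balance.

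**Inputs from the protocol:** entry above 1000 ml (item 2(2)); at least 200 ml per tap (4(1)); 100 ml saline per dose (4(2)); dosing every 2 weeks, 1–4 times (4(6)); CT before treatment and at weeks 4 and 8 (8(1), 8(3)).

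**Assumptions:** a 2000 ml baseline, a true rise of 50% and a 2000 ml drain for the large-drain example; regrowth half-time *h* of 3 or 7 days. The Abstract says only that drained ascites returns fast and gives no rate.

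**1. Schedule.**
- First-dose origin: doses and taps fall on days 0, 14, 28 and 42, and CTs on days 28 and 56. The third tap coincides with the week-4 CT for anyone given three or more doses.
- Last-dose origin with *n* doses: the week-4 CT is on day 14(n−1)+28 = 28, 42, 56 or 70, and the week-8 CT on day 14(n−1)+56 = 56, 70, 84 or 98.
- If 1–4 times means repeats after the first dose, a fifth tap falls on day 56, the week-8 CT date under first-dose origin.

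**2. CT after a minimum tap at the same visit.** Extra shift = 200/baseline: 20, 10 or 7 percentage points at 1000, 2000 or 3000 ml. If the CT also follows the infusion, (200−100)/baseline: 10, 5 or 3 points.

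**3. Minimum taps, CT first, first-dose origin.** Deficit left at CT = Σ 200 × 2^(−days since tap/h).
- Week 4 (taps on days 0 and 14): h = 7 gives 12.5 + 50 = 62.5 ml; h = 3 gives 0.3 + 7.9 = 8.2 ml.
- Week 8 (taps on days 0, 14, 28 and 42): 66.4 ml (h = 7) and 8.2 ml (h = 3).
- At 1000 ml this is about 0.8–6% at week 4 and 0.8–7% at week 8. It is about half that if the saline is credited, and one third at 3000 ml.

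**4. Large drain *k* days before a CT.** Baseline 2000 ml, true volume 3000 ml, 2000 ml drained. Reading = (3000 − 2000 × 2^(−k/h) − 2000)/2000. Break-even drain = 1000 × 2^(k/h).

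| Days before CT | Reading, h = 3 | Reading, h = 7 | Break-even, h = 3 | Break-even, h = 7 |
|---|---|---|---|---|
| 1 | −29% | −41% | 1260 ml | 1104 ml |
| 3 | 0% | −24% | 2000 ml | 1346 ml |
| 7 | +30% | 0% | 5040 ml (more than is present) | 2000 ml |

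A 1000 ml drain one day before does not reverse the sign: the reading is +10% (h = 3) or +5% (h = 7).

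**5. Early drain.** 2000 ml drained on day 1 leaves 2000 × 2^(−27/h) = 4 ml (h = 3) to 138 ml (h = 7) at day 28, and under 10 ml at day 56. Distance from the CT decides whether a drain matters.

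**6. Baseline CT after the first tap.** If that CT also sets eligibility, the smallest case is about 1200 ml before and 1000 ml after the tap. With no true change, the week-4 reading is (1200 − 62.5 − 1000)/1000 = +14% (h = 7) to (1200 − 8.2 − 1000)/1000 = +19% (h = 3), saline ignored.

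**The case against.** **The natural reading closes part of the gap.** The baseline CT sits in the pre-treatment work-up, and CT is the only volume measure named, so a CT before the first tap is the likely intention. A reader might compute +17% to +24% for an unchanged 1000 ml patient scanned after the tap, but that uses an 800 ml baseline, which would fail entry if the same CT sets eligibility. Item 7(3) names the last dose when it means it ("Outpatient clinic every week till 2 weeks after the last dose of medication; then every one month for 6 m"), which favours a first-dose origin for the CTs. These readings are plausible, but neither is written down, and the first-dose reading is the one that puts a tap on the week-4 CT date.

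**Heavy drainage on study is speculative.** This stands in part. The Background describes repeated paracentesis in the hospital's refractory patients, and a reader might infer that it will be common here. Patients already receiving it are excluded, so that passage gives no rate for this trial. But an entry exclusion is not an on-study rule, and later drainage remains possible. A reader might also infer that drainage will go unrecorded. The protocol does not say so; it only does not require the record.

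**Scoring belongs in the analysis plan.** That is fair for scoring, and a plan not seen here may cover it. An analysis plan cannot restore the order of CT and tap, or guarantee volumes and dates that the protocol never required.

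**Conclusion.** The point holds in a limited form and should be fixed. The protocol leaves CT–tap order and the origin of weeks 4 and 8 open, and it neither requires on-study drainage to be recorded nor separates it from drug effect, in a study with no comparator described. The sizes differ sharply by case:

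- up to 20 percentage points at a 1000 ml baseline for a same-visit CT after a minimum tap (10 after the infusion);
- about 0.8–7% for minimum taps when the CT comes first;
- a reversed sign for a large drain within days of a CT (−29% to −41% instead of +50% in the example).

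The last two rest on the assumed half-times, and the last also on the assumed baseline, growth and drain. A reader might conclude that the routine taps alone make the endpoint uninterpretable. The figures do not support that: a large, sustained fall without extra drainage stays informative.

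**What to change.** On the measurement side only, without altering when or how much any patient is drained:

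1. State whether weeks 4 and 8 count from the first or the last dose.
2. Take the baseline CT before the first tap, and do the CT before any sampling tap due at the same visit.
3. Record the date, volume and purpose of every fluid removal, including at the first dose, and the volume infused. Enter the purpose before the CT is read.
4. State in advance that a CT fall preceded by non-sampling drainage within a pre-specified interval is not attributed to the drug in the primary analysis. Cover drainage between the baseline CT and the first dose too, because a pre-tap baseline does not reflect it. Say what the rule means for a yes/no and for a volume endpoint. As sensitivity analyses, report the CT change with and without such patients, together with the volumes drained.

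Do not score every drain after the first dose as failure; step 5 of the working shows that an early drain has almost no effect on a later CT under these half-times.

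The cost is a few form fields, a few lines of protocol text and a possibly less favourable reported reduction.
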